Study conclusion						●	See Section 4.4 for details

Note: The double-line borders indicate the analyses which will be performed on all data (i.e., data that are as clean as possible) obtained up to these timepoints.

AE = Adverse event; AESI = Adverse event of specific interest; AF = Atrial fibrillation; CMI = Cell-mediated immunity; eCRF = electronic case report form; pIMDs = Potential immune-mediated diseases; RSV = Respiratory Syncytial Virus; SAE = Serious adverse event; SoC = Standard of care; WOCBP = Women of childbearing potential.

- is used to indicate a study procedure that requires documentation in the individual eCRF.
- is used to indicate a study procedure that does not require documentation in the individual eCRF.

^a Visit 2 is planned in the CMI subset of the study population (30% of the group population i.e., 38 participants in the group, at the designated CMI sites).

^b Vital signs, urine sample for pregnancy test and blood sampling for RSV neutralizing titers, CMI and CCI must be taken on the same day, prior to study intervention administration. If the study intervention administration is delayed by any reason, the vital signs and samples (both blood and urine) will need to be collected again on the day of study intervention administration, urine pregnancy test needs to be repeated, and the first blood sample will be destroyed.

^c Participants must bring their diary cards at this visit for review, and the same would be re-dispensed to them.

^d AF will be considered as AESI in this study and will be additionally reported in the AF follow-up questionnaire (electronic or paper) in eCRF. The collection of AF will be performed following the AE/SAE reporting periods. The reporting of non-serious AF will be performed according to the unsolicited AE reporting period. The reporting of AF meeting the SAE definition (serious AF) will be performed according to the SAE reporting period.

Under special circumstances, home visits may be conducted at the discretion of the investigator (Refer to Section 8 for details).

Table 4 Intervals between study visits for IC 1-dose group (RSV_IC_1)

Interval	Planned visit interval	Allowed interval range
Screening Visit → Visit 1	-7 days	-30 to -7 days
Visit 1 → Visit 2*	7 days	7 - 14 days
Visit 1 → Visit 3	30 days	30 - 60 days
Visit 3 → Visit 4	30 days	30 - 42 days
Visit 1 → Visit 5	180 days	180 - 210 days
Visit 1 → Visit 6	365 days	350 - 380 days

* Only in the CMI subset.

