Table 5 Intervals between study visits for IC 2-dose group (RSV_IC_2)

Interval	Planned visit interval	Allowed interval range
Screening Visit → Visit 1	-7 days	-30 to -7 days
Visit 1 → Visit 2*	7 days	7 - 14 days
Visit 1 → Visit 3	30 days	30 - 60 days
Visit 3 → Visit 4	30 days	30 - 42 days
Visit 3 → Visit 5	180 days	180 - 210 days
Visit 3 → Visit 6	365 days	350 - 380 days

* Only in the CMI subset.

Table 6 Intervals between study visits for healthy participant group (RSV_HA)

Interval	Planned visit interval	Allowed interval range
Visit 1 → Visit 2*	7 days	7 - 14 days
Visit 1 → Visit 3	30 days	30 - 60 days
Visit 3 → Visit 4	30 days	30 - 42 days
Visit 1 → Visit 5	180 days	180 - 210 days
Visit 1 → Visit 6	365 days	350 - 380 days

* Only in the CMI subset.

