6.2. Preparation, handling, storage, and accountability

The investigator or designee must confirm appropriate conditions (e.g., temperature) have been maintained during transit for all study intervention received, and any discrepancies are reported and resolved before use of the study intervention.

Only participants enrolled in the study may receive study intervention, and only authorized site staff may supply, prepare, or administer study intervention. If allowed by country regulation/ethics, study intervention may be administered by a HHS professional.

All study intervention must be stored in a secure, environmentally controlled, and monitored (manual or automated) area in accordance with the labeled storage conditions with access limited to the investigator and authorized site staff.

The investigator, institution, the head of the medical institution (where applicable), or authorized site staff is responsible for study intervention accountability, reconciliation, and record maintenance (i.e., receipt, reconciliation, and final disposition records).

Further guidance and information for the final disposition of unused study interventions are provided in the pharmacy manual.

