6.5. Study intervention compliance

Participants will receive study intervention at the site, directly from the investigator or designee, under medical supervision. The date and time of each dose administered in the clinic will be recorded in the source documents.

A record of the quantity of RSVPreF3 OA Investigational Vaccine administered to each participant must be maintained and reconciled with study intervention and compliance records.

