7. DISCONTINUATION OF STUDY INTERVENTION AND PARTICIPANT DISCONTINUATION/WITHDRAWAL

7.1. Discontinuation of study intervention

Discontinuation of study intervention refers to any participant who has not received all planned doses of the study intervention. In rare instances, it may be necessary for a participant to permanently discontinue study intervention. If study intervention is permanently discontinued, the participant should, if possible, continue other study procedures (e.g., safety or immunogenicity), planned in the study protocol at the discretion of the investigator.

The primary reason for premature discontinuation of the study intervention will be documented in the eCRF based on the list below:

Reasons	Additional items/Sub-reasons
AE	Unsolicited AE
	Solicited AE
	SAEs / pIMDs /AESIs
Lost to follow-up	
Withdrawal by Participant	Burden of Procedure
	Participant Relocated
	COVID-19

Reasons	Additional items/Sub-reasons
	Other, Specify
Investigator Decision	Specify
Protocol Deviation	Specify
Site Terminated by Sponsor	
Study Terminated by Sponsor	
Pregnancy	
Death	
Other	Specify

AE = Adverse event; AESI = Adverse event of special interest; COVID-19 = Coronavirus disease; pIMD = Potential immune-mediated disease; SAE = Serious adverse event.

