 - Caregivers may help the study participants with performing some practical study procedures such as receiving or making phone calls to site staff, planning study visits, transcribing responses to diaries, transportation to and from the study site etc. However, at no time, the caregiver should evaluate the participant's health status while answering diaries or make decisions on behalf of the participant. At the first study visit, the site staff should inform the participant of the possibility to appoint a caregiver. Then at subsequent study visit(s), the site staff should check again with the participants if they wish to appoint a caregiver or if there were or will be changes of caregiver.
- In the event of a significant study-continuity issue (e.g., caused by a pandemic), alternate strategies for participant visits, assessments, study intervention distribution and monitoring may be implemented by the sponsor or the investigator, as per local health authority/ethics requirements.
- It is preferred to have all visits on-site. However, during special circumstances (e.g., COVID-19 pandemic, SOT patients in whom health has deteriorated during the study, or for whom the transfer to the clinic has become very difficult), the specific guidance from local public health, if applicable, and other competent authorities regarding the protection of individuals' welfare must be applied and consulted with the sponsor. For the duration of such special circumstances, the following measures may be implemented for enrolled participants:

- Follow-up visits (Visit 3 in HA and IC 1-dose groups, and Visits 2, 4, 5, and 6 for all groups) may be conducted at the participant's home (by the site staff or by a home care service system), if appropriate. If home visits are not possible, telephone calls or other means of virtual contacts may be used.
- Diary cards may be transmitted from and to the site by electronic means or courier service if allowed by local regulations and or conventional mail or collected at home. Biological samples may be collected at participant's home. Biological samples should not be collected if they cannot be processed in a timely manner or appropriately stored until the intended use. Home Visits are not allowed for participants in the CMI subset (due to time-sensitivity of CMI samples) except in special circumstances and with the prior approval of the GSK central study team.

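### Section 8 allows an off-site Visit 3 in RSV_HA and RSV_IC_1 but not in RSV_IC_2, so the post-dose-1 sample of a participant who cannot travel may be lost in one randomised arm and kept in the other

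*Protocol*

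**What the plan says.** **Off-site visits.** Section 8 prefers visits at the site but relaxes this in special circumstances. One of its examples is "SOT patients in whom health has deteriorated during the study, or for whom the transfer to the clinic has become very difficult". The relief reads: "Follow-up visits (Visit 3 in HA and IC 1-dose groups, and Visits 2, 4, 5, and 6 for all groups) may be conducted". The setting it goes on to name is the patient's own home, with telephone or virtual contact as the fallback. Visit 3 of RSV_IC_2 does not appear in that list.

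**Visit dates.** For RSV_IC_2, Table 5 dates every later visit from Visit 3, for example "Visit 3 → Visit 5" at 180-210 days. For RSV_IC_1, Table 4 dates Visits 5 and 6 from Visit 1 ("Visit 1 → Visit 5"), but its Visit 4 also runs from Visit 3 ("Visit 3 → Visit 4"). No substitute date is given if Visit 3 is missed.

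**After a missed dose.** Section 7.1 says "the participant should, if possible, continue other study procedures (e.g., safety or immunogenicity), planned in the study protocol".

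**Place of dosing.** Section 6.2: "If allowed by country regulation/ethics, study intervention may be administered by a HHS professional". Section 6.5: "Participants will receive study intervention at the site, directly from the investigator or designee, under medical supervision". The Table 2 footnote permits home visits in RSV_IC_2 at the investigator's discretion without excepting Visit 3, and refers to Section 8.

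**Use of Visit 3 data.** Table 7 and Section 9.3.2 pool RSV_IC_1 and RSV_IC_2 at Visit 3 for the GMT ratio against RSV_HA and for the MGI over Visit 1.

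**The concern.** The two IC arms are randomised and treated alike until dose 2, so up to and including the Visit 3 blood draw they should be followed under the same rules. They are not: the same event, a deteriorated patient who cannot travel, allows an off-site visit in one arm and, on the face of Section 8, not in the other.

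The injection explains why the visit was left out, but the visit also holds procedures that do not depend on it: the neutralising titre draw, return of the dose 1 diary, and recording of SAEs, pIMDs and transplant AESIs. Some of the patients who trigger the home-visit rule will be ones whom Section 7.1.1 bars from a further dose, so for them only these procedures remain.

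At stake is a loss of post-dose-1 titres that depends on arm and probably on health. It would remove some of the frailest, possibly lowest-responding, patients from half of the pooled IC group that is compared with healthy adults at Visit 3.

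**Working it through.** **1. The plan's own figures (Section 9.5.1).** With a noncentral t calculation, a paired test, one-sided alpha 2.5% and n = 100, the detectable fold-increases are 1.385, 1.458, 1.298 and 1.352, against 1.39, 1.46, 1.30 and 1.35 in Table 21. For the pooled Visit 3 comparison (100 healthy, SD 0.45; 200 IC, SD 0.50), a Welch t-test gives 80.2% power at 1.45-fold against the stated 80%. Enrolment is 100/0.80 = 125 per group, as stated. No number in the plan is disputed.

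**2. Which analyses a missed RSV_IC_2 Visit 3 reaches.**

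| Analysis | Needs | Effect of the home-visit rule |
|---|---|---|
| Pooled IC GMT ratio and MGI at Visit 3 | dose 1 and Visit 3 serum | direct |
| Primary MGI, Visit 4 over Visit 3, RSV_IC_2 | Visit 3 serum and dose 2 | little or none: a participant without dose 2 has no post-dose-2 response to contribute |
| RSV_IC_2 titres at Visits 4-6, PPS | dosing per protocol (Table 20) | little: an undosed participant would probably leave the PPS anyway |
| Safety percentages to Visit 6, Exposed Set | continued contact | indirect, through undated Visits 4-6 |

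**3. Precision.** The documents give no rate of non-attendance, so the counts are assumptions. With k further RSV_IC_2 samples lost beyond the planned 20% attrition, power of the pooled comparison at 1.45-fold is:

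| k | IC n | Power |
|---|---|---|
| 0 | 200 | 80.2% |
| 2 | 198 | 80.0% |
| 5 | 195 | 79.8% |
| 10 | 190 | 79.4% |

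**4. Selection.** Assume that a fraction f of each IC arm is frail with a GMT r-fold lower, and that these patients are lost from RSV_IC_2 only. The RSV_IC_2 GMT then rises by r^f. With equal arms, the pooled log mean moves from −f·log r to −f·log r/(2 − f), so the pooled GMT rises by r^[f(1 − f)/(2 − f)].

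- f = 0.02, r = 1.5: arm 1.5^0.02 = 1.008; pooled 1.5^0.0099 = 1.004.
- f = 0.05, r = 2: arm 2^0.05 = 1.035; pooled 2^0.0244 = 1.017.
- f = 0.10, r = 3: arm 3^0.10 = 1.116; pooled 3^0.0474 = 1.053.

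The RSV_HA over pooled IC ratio falls by the same pooled factor. For scale, the standard error of that log10 ratio is sqrt(0.45²/100 + 0.50²/200) = 0.0572, so its 95% limits lie a factor of about 10^(1.96 × 0.0572) = 1.295 either side of the estimate.

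**5. Dates for Visits 4-6 when Visit 3 is missed.** All in days after Visit 1:

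| | Visit 4 | Visit 5 | Visit 6 |
|---|---|---|---|
| RSV_IC_2, Visit 3 attended on Day 30-60 | 60-102 | 210-270 | 380-440 |
| Dated from the planned Visit 3 (Day 30) | 60-72 | 210-240 | 380-410 |
| Dated from Visit 1 as in RSV_IC_1 | – | 180-210 | 350-380 |

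Dating from the planned Visit 3 keeps the participant inside the range of the randomised arm. Dating from Visit 1 ends follow-up 30 to 60 days earlier.

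**The case against.** The strongest defence is that the omission follows from the design. The clause concerns follow-up visits, and Visit 3 of RSV_IC_2 is a dosing visit with a contraindication check, injection and 30-minute observation; Visit 1 is unlisted for the same reason. There is also relief elsewhere. The window is 30 days wide. The next bullet in Section 8 lets diaries be sent in and samples be drawn at home without naming a group, and the Table 2 footnote does not except Visit 3. All this stands, and it makes loss of the sample possible rather than certain. It does not remove the problem: the sentence that names visits and groups leaves this one out, and the footnote defers to that section.

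Four stronger readings are tempting, and the documents do not support them.

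- **That the RSV_IC_1 counterpart is safely retained.** A telephone contact yields no titre, PPS status of off-site visits is decided case by case, and home visits in the CMI subset need special circumstances and prior approval. A missed Visit 3 leaves Visit 4 undated in RSV_IC_1 and RSV_HA too.
- **That RSV_IC_2 participants drop out of safety follow-up and count as event-free.** Visits 4-6 may be at home or by telephone in every group, Section 7.1 keeps undosed participants in other procedures, and under Section 7.3 one missed visit is not loss to follow-up.
- **That the primary analysis is biased.** It needs dose 2, so the home-visit rule hardly touches it.
- **That undosed RSV_IC_2 participants should be re-dated from Visit 1 to match RSV_IC_1.** No such comparison is planned, and it would shorten safety follow-up for part of an arm that the Exposed Set analyses as randomised.

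**Conclusion.** The point holds in a limited form. Section 8 applies a different off-site rule at Visit 3 to two arms that should be handled alike at that point, and it does so for the whole visit when only the injection distinguishes them. The consequence is a possible arm-dependent loss of post-dose-1 titres, confined mainly to the pooled IC Visit 3 GMT ratio and MGI.

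Its size is small: under 1 percentage point of power for up to 10 extra losses, and at most about 5% on the pooled GMT in the most adverse scenario tried. Both rest on assumed counts and assumed response differences. The missing date for Visits 4-6 is by itself a minor omission. The conflict over where dose 2 may be given is a separate inconsistency; Section 6.2 can be read as a conditional exception to Section 6.5, but the text does not say so.

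The change is worth making because it is cheap and removes an avoidable difference between randomised arms, not because the trial's conclusions are at risk.

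**What to change.** 1. **Section 8:** add Visit 3 of RSV_IC_2 to the off-site list for its non-dosing procedures only (titre draw, diary return, SAE/pIMD/AESI collection), on the terms already given to the other groups.
2. **Tables 2 and 5:** add a footnote that, if Visit 3 is missed, Visits 4-6 are dated from its planned date, so that follow-up stays aligned with the randomised arm. Do not re-date Visits 5-6 from Visit 1.
3. **Sections 6.2, 6.5 and 8 and the Table 2 footnote:** reconcile what they say about where dose 2 may be given. This review takes no position on which is right.

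The cost is one clause, one footnote and one reconciliation, plus a few home draws or calls through arrangements that the protocol already provides for. Sample size and analyses do not change.

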8.1. Administrative and baseline procedures

8.1.1. Collection of demographic data

Record demographic data such as year of birth, age at the time of study intervention administration, sex, race*, and ethnicity* in the participant's eCRF.

Collection of sex, race and ethnicity data is necessary to assess and monitor the diversity of the trial participants, and to determine if the trial participants are truly representative of the impacted population.

*Differences in the safety and efficacy of certain medical products, including vaccines [Haralambieva, 2013; Pérez-Losada, 2009; Kollmann, 2013] have been observed in racially and ethnically distinct subgroups. These differences may be attributable to intrinsic factors (e.g., genetics, metabolism, elimination), extrinsic factors (e.g., diet, environmental exposure, sociocultural issues), or interactions between these factors. Therefore, both geographic ancestry (race) and ethnicity will be collected for all study participants.

Age is collected to stratify the population and determine the impact of the study intervention by age.

8.1.2. Medical/vaccination history

Obtain the participant's relevant medical/vaccination history by interviewing the participant/participant's parent(s)/LAR(s) and/or review of the participant's medical/vaccination records. Record any relevant pre-existing conditions, signs and/or symptoms present prior to the study intervention in the eCRF.

Any vaccine administered up to 1 year before study vaccine administration should be recorded in the eCRF with date of vaccination. For history of influenza vaccination, information about the vaccine formulation (e.g., adjuvanted or non-adjuvanted or highdose) should be recorded.

Administration of *Shingrix* at any timepoint (even if longer than 1 year before the study vaccine administration) should be recorded in the eCRF. The date of vaccinations should be collected and recorded in the eCRF.

Specifically additional data will be collected for transplant participants as listed in Section 8.1.3.

8.1.3. Record specific participant transplant information

The following information will be recorded (if available in medical history of the lung/renal transplant recipient patient) and entered into the eCRF at screening visit:

Current transplant history

Information will be collected and entered eCRF about the current transplant, including:

- Type of transplant (one or two kidneys, one or two lungs)
- Date of transplantation
- Biopsies since transplantation (Yes/No), and if yes,
 - collect the results indicating rejection and type of rejection (Acute or Chronic)
- Current allograft function with options (stable for 3 to \leq 6 months, stable for 6 to \leq 12 months, or stable for $>$ 12 months)

Previous transplant

Information will be collected and entered eCRF about the previous transplants (if any before the current), including:

- Type of transplant (one or two kidneys, one or two lungs)
- Date of transplantation
- Data about allograft loss (Yes/No), and if yes,
 - collect the reasons for allograft loss

In case of multiple previous transplantations, all previous transplantations should be recorded with the information as above.

8.1.4. Record height and weight

Measure the participant's height and weight and record the values in the eCRF.

8.1.5. Targeted physical examination/history-directed physical examination

A history-directed physical examination will be performed for each participant at the screening visit in SOT patients and Visit 1 in healthy participants. At each subsequent visit, a targeted physical examination will be performed, as needed.

If the investigator determines that the participant's health on the day of study intervention administration temporarily precludes dosing, the visit will be rescheduled. Refer to Section 5.5 for the list of criteria for temporary delay of study intervention administration. Treatment of any abnormality observed during this examination has to be performed according to local medical practice outside this study or by referral to an appropriate health care provider.

Collected information needs to be recorded in the eCRF.

A targeted physical examination at each study visit after the first study intervention administration will be performed if part of the SoC or only if the participant/participant's parent(s)/LAR(s) indicates during questioning that there might be some underlying pathology(ies) or if deemed necessary by the investigator or delegate.

8.1.6. Vital signs

At minimum, temperature, vital signs (e.g., heart rate, respiratory rate, and blood pressure) will be recorded.

Vital signs are to be taken after at least 10 minutes of rest and before blood collection for laboratory tests (if applicable) and will consist of systolic/diastolic blood pressure, heart rate and respiratory rate by counting the number of breaths for 1 minute before vaccination at Visit 1 and Visit 3.

Blood pressure and pulse measurements will be assessed with a completely automated device. Manual techniques will be used only if an automated device is not available.

In case of increased blood pressure (i.e., systolic BP ≥ 140 mm Hg, and /or diastolic BP ≥ 90 mm Hg) the measurements of 3 consecutive blood pressure readings will be recorded at intervals of at least 1 minute. The average of the 3 blood pressure readings will be recorded [Smith, 2005].

Collected information needs to be recorded in the eCRF.

If the investigator determines that the participant's health on the day of study intervention administration temporarily precludes dosing, the visit will be rescheduled. Vital signs will be re-taken in case of delayed vaccination. Refer to the Section 5.5 for the list of criteria for temporary delay of study intervention administration.

The body temperature of each participant needs to be measured prior to study intervention administration and recorded in the eCRF. The location for measuring temperature will be oral or axillary. If the participant has fever (defined as temperature $\geq 38.0^{\circ}\text{C}/100.4^{\circ}\text{F}$ regardless of the location of measurement) on the day of study intervention administration, the visit will be rescheduled (refer to Section 5.5 for details).

